accredited center, with purposeful sampling in order to achieve approximately the same overall sample size in each of the 6 risk group x treatment cohorts. By randomly selecting a small number of patients from a large number of institutions, we can ensure a broadly representative sample of hospitals and patients, ideal for CER.

Outcomes [RQ-6]: The NCDB annually collects vital status (survival), cancer status (disease free or recurrence), date of recurrence, and treatments for recurrent cancer. This will allow for evaluation of our primary outcome of overall survival, and secondary outcomes of time to recurrence and treatment for recurrent cancer. Additional secondary outcomes will be collected by the special studies mechanism, and include: rates and types of procedures (e.g. biopsy) and tests (e.g. advanced imaging), results of these tests, and treatment for recurrent cancer.

The special studies mechanism will also confirm existing NCDB information regarding cancer status and date of recurrence. Specifically, the PSA dates and results will be abstracted from medical records. Therefore, the investigators are able to define recurrence per standard definitions. These citations provide official definitions for biochemical recurrence after radiation treatment¹⁶ and radical prostatectomy.¹⁷

Cancer registry staff will review hospital and provider records to collect these data, using the same rigorous procedures as primary registry data with specific instructions and training for abstraction by the investigative team and personnel at CoC. These data will be combined with the existing NCDB data to provide the analysis dataset. This Table summarizes the data elements (outcomes) to be collected using the special studies mechanism: (Table 1)

Data Point	Format
Date of imaging	mm/dd/yy
Type of imaging performed	1) bone scan; 2) CT scan; 3) MRI; 4) X-ray; 5) PET scan; 6) other
Date of biopsy/procedure	mm/dd/yy
Biopsy/procedure results	1) benign; 2) malignant; 3) indeterminate
Date of treatment for recurrence	
Type of treatment	1) radiation; 2) surgery; 3) hormone therapy; 4) chemotherapy; 5) other therapy; 6) no treatment

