The full description of all the variables which will be collected is provided in a separate document. Of note, we will first undergo a pilot study with a limited number of participating sites to test the feasibility of collecting each data element retrospectively. Lessons from the pilot study will inform necessary modifications of data elements collected before embarking on the full with sites across all CoC-accredited centers.

Covariates [IR-3][CI-4]: Data collected at time of diagnosis by the NCDB include, but are not limited to, the following:

- *Demographics:* age, race/ethnicity, marital status, county of residence, census tract data, occupation, tobacco history, rural/urban continuum, insurance

- *Cancer specific variables*: histology/behavior (ICD-0-2, ICD-0-3), diagnostic date. Starting in 2004: PSA level, Gleason score and clinical stage – used to classify patients into low-, intermediate-, and high-risk categories.⁷
- *Comorbidities*: Up to 10 per patient are abstracted and scored per the Charlson-Deyo comorbidity score.¹⁸
- *Hospital characteristics*: unique facility identifier, type of cancer center
- *First course of treatment*: surgery, radiation, hormonal/endocrine, treatment dates.

[figure not shown]
Data Analysis [IR-3]: Patients diagnosed in 2005-2007 will be included. By the time of data analysis, the NCDB will have survival data through 2015, providing 8-10 years of follow-up data for each patient.

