The analysis is stratified by two important factors, risk of recurrence (low, intermediate, high) and type of initial treatment (surgery, radiation); thus, 6 separate analyses will be performed. All outcomes will be defined from years 2-10 from end of prostatectomy or radiation treatment (Figure 1). We will use two modeling strategies to evaluate our outcomes of interest: 1) modified Poisson/binary regression^{19,20} with sandwich standard errors to estimate risks of the events of interest during a set follow-up period; and 2) Cox Proportional Hazards regression [CI-3]. Using the modified Poisson/binary regression models, we will estimate the risk of experiencing the outcome of interest (death, recurrence, use of procedures and tests, treatment for recurrence) during a defined interval beginning in the second year following treatment. Additionally, we will estimate overall survival using adjusted Cox Proportional Hazards regression models. We will evaluate the proportional hazards assumption by generating Kaplan-Meier survival curves and through testing interactions between relevant covariates and time in the Cox model. Covariates that violate the proportional hazards assumption will be used as stratification variables as appropriate. In sensitivity analyses, we will generate a propensity score (where the patient, provider and hospital characteristics measured at the time of prostatectomy or radiation completion are included in the propensity score) and create a matched cohort of patients to evaluate using Kaplan-Meier survival models [described in detail in C3]. For secondary outcomes, time to recurrence will be modeled for each surveillance frequency using a competing risk analysis as described by Fine and Gray.²¹ Similar methods will be used to calculate the cumulative incidence of procedures and tests and treatment for recurrence.

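### Procedures and tests are named as rates and as a harm to be quantified, but only any use and first-event cumulative incidence are planned, so repeat use is not analysed

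*Combined protocol and SAP*

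**What the plan says.** In Specific Aim 1, Outcomes [RQ-6], the secondary outcomes gathered by special study include "rates and types of procedures (e.g. biopsy) and tests (e.g. advanced imaging"). Table 1 in that section has the fields "Date of imaging" and "Date of biopsy/procedure", and codes imaging as "1) bone scan; 2) CT scan; 3) MRI; 4) X-ray; 5) PET scan; 6) other". It does not say whether one date or every date is recorded for a patient. The next paragraph adds that "The full description of all the variables which will be collected is provided in a separate document".

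The Aim 1 objective sets survival as the benefit and procedures, tests and treatments as the harms to be quantified. The Aim 1 hypothesis is that more frequent surveillance raises receipt of procedures and tests.

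Data Analysis [IR-3] gives two analyses for this outcome:

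- Modified Poisson/binary regression: "we will estimate the risk of experiencing the outcome of interest (death, recurrence, use of procedures and tests, treatment for recurrence"). The period covered starts in year 2 after treatment, but its length is not given.
- After the Fine and Gray analysis of time to recurrence: "Similar methods will be used to calculate the cumulative incidence of procedures and tests and treatment for recurrence".

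Section C3 applies propensity-score weighting and matching to all outcomes, but brings in no new outcome scale.

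**The concern.** Modified Poisson regression, as used here, is a risk model for a yes/no outcome, not a count model. Cumulative incidence of this kind runs to the first event. Under both, a man who has one scan and a man who has ten contribute the same event. The outcome is named in terms of rates and date fields exist, yet nothing in the plan uses the second or any later event.

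This matters because repeated work-up is one way in which frequent PSA testing could burden patients. An any-use ratio answers how many men have at least one procedure or test. It does not answer how many procedures or tests they have. When most men in every group have at least one, the any-use ratio moves towards 1 even if the amount of testing differs substantially. A reader weighing survival against harm could then take a small any-use ratio for a small difference in burden.

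**Working it through.** The documents give no frequency, effect size or power for procedures and tests, so there is no planned figure to reproduce. The check asks how far an any-use analysis departs from a count analysis across a range of assumed rates.

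**Window.** Diagnoses are from 2005-2007 and survival data run through 2015: 2015 − 2007 = 8 and 2015 − 2005 = 10 years, which matches the plan's stated follow-up. Year 1 defines exposure, which leaves about 7 to 9 years. I use T = 8.

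**Group sizes.** The plan has 2,333 men per cohort. The Table 2 high-risk shares for the least and most frequent groups are 17% and 30%: 0.17 × 2,333 = 397 and 0.30 × 2,333 = 700.

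**Formulas.** With yearly rate r, the mean count is m = rT. The chance of any use is 1 − exp(−m), or 1 − (1 + km)^(−1/k) with gamma frailty variance k. Competing death is ignored.

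**Attenuation (assumed true rate ratio 1.5, T = 8).** Example at 0.2 v 0.3 per year: m = 1.6 and 2.4, so any use is 1 − e^(−1.6) = 0.798 and 1 − e^(−2.4) = 0.909, a ratio of 1.14.

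| Lower rate per man-year | Any use, k = 0 | Risk ratio, k = 0 | Risk ratio, k = 1 |
|---|---|---|---|
| 0.02 | 15% v 21% | 1.44 | 1.40 |
| 0.1 | 55% v 70% | 1.27 | 1.23 |
| 0.2 | 80% v 91% | 1.14 | 1.15 |
| 0.5 | 98% v >99% | 1.02 | 1.07 |

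**Power (assumed rate ratio 1.2, k = 1, 397 v 700, two-sided 5%).** Power is Φ(|ln R| / SE − 1.96), where R is the risk ratio or the rate ratio.

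- Any use: SE² = (1 − p₀)/(397p₀) + (1 − p₁)/(700p₁).
- Count: SE² = (1/m₀ + k)/397 + (1/m₁ + k)/700.

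Example at 0.2 per year, with m₀ = 1.6 and m₁ = 1.92:

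- Any use: p₀ = 1.6/2.6 = 0.615 and p₁ = 1.92/2.92 = 0.658. The risk ratio is 1.07, ln R = 0.066, SE = 0.048, and power is 28%.
- Count: ln 1.2 = 0.182, SE = 0.079, and power is 63%.

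| Lower rate per man-year | Power, any use | Power, count |
|---|---|---|
| 0.02 | 17% | 20% |
| 0.1 | 30% | 50% |
| 0.2 | 28% | 63% |
| 0.3 | 25% | 69% |

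At 0.2 per year the result hardly depends on the window: 29% v 61% over 7 years and 27% v 65% over 9.

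**Time to first event.** This is closer to the planned cumulative-incidence analysis. A simulated log-rank test under the same assumptions (397 v 700, rate ratio 1.2, k = 1, 8 years) has power of about 35% at both 0.2 and 0.3 per year. That is somewhat above any use and well below the count.

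**The case against.** The strongest reply is that any use is a legitimate estimand and fits the hypothesis, which speaks of receipt. The word rates can also be read as proportions. That stands: the planned analyses are valid and should stay. They leave the amount of use unmeasured, although the objective is to quantify this harm.

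A reader might infer several stronger things that the documents do not support.

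- **That the analysis will saturate.** No event rate is given, and the binary model's interval may be short. At 0.2 v 0.3 per year with frailty variance 1, the risk ratio is 1.31 over 2 years against 1.15 over 8. At 0.02 per year over 8 years, with a rate ratio of 1.5 and no over-dispersion, power is 74% for any use against 79% for counts, so little is lost. Such low rates are plausible for biopsy in the low-risk cohorts, where the plan puts recurrence below 10%. The imaging list includes X-ray and an open category, but nothing says that all types will be pooled.
- **That a real effect would be missed.** With a rate ratio of 1.5 at 0.2 per year and 397 v 700 men, any-use power is above 99% without over-dispersion and 84% with frailty variance 1. The difference of 62% v 71% in the latter case is reportable in itself. The serious power loss arises with smaller effects.
- **That cumulative incidence fails exactly as any use does.** It keeps the timing of the first event. With no between-patient variation, 0.5 events per year, a rate ratio of 1.25 and the low-risk groups (467 v 443), first-event power is 92% against 34% for any use. Much of that advantage goes when men differ in their propensity to be tested, as the simulation shows, and repeats are ignored either way.
- **That this is the main harm, or that the dates needed are already in hand.** The plan lists procedures and tests alongside treatments, as secondary outcomes. Abstraction is still to come, and Table 1 does not promise every date.

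**Conclusion.** The gap is real. An outcome described in terms of rates, and set down as a harm to be quantified, has no analysis that uses repeat events. Its cost depends on how common use is. For uncommon events the planned measures lose little. From about 0.1 events per man-year the attenuation is visible: a true rate ratio of 1.5 appears as an any-use ratio of 1.27, falling to 1.14 at 0.2 and 1.02 at 0.5. For a rate ratio of 1.2, counts have roughly 1.7 to 2.3 times the power of any use at 0.1 to 0.2 per year (50/30 and 63/28).

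These sizes rest on assumed rates, an assumed frailty variance, an 8-year window and no competing death. The absence of a count or recurrent-event analysis rests on the text alone.

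**What to change.** - Keep the any-use and cumulative-incidence analyses, and state the length of the interval for the binary model.
- Add, for each type of procedure or test, the number per man-year from the start of year 2: negative binomial or log-link count regression with a person-time offset and robust standard errors, using the covariates and propensity-score sensitivity analyses already planned.
- Show it with a mean cumulative count curve by surveillance group, treating death as a terminal event.
- Use the planned pilot to confirm that all event dates, not only the first, can be abstracted, and say so in the variable list before full collection starts.

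The cost is a short addition to the SAP and modest programming. If only one date per patient is now captured, there is also more abstraction work at the sites, so this is best settled at the pilot stage.

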- High-risk prostate cancer (defined by clinical stage \geq T3, PSA >20, or Gleason 8-10): most aggressive type of prostate cancer. Recurrence risk is ~50%.⁷ Two cohorts will be examined separately, 5) those treated with **initial prostatectomy**, and 6) those treated with **initial radiation**.

[figure not shown]
The objective of this aim is to quantify the potential benefits (survival) and harms (procedures/tests, treatments) of different PSA surveillance frequencies in the 6 patient groups, which are currently unknown. It is intuitive that more frequent surveillance will lead to more findings of elevated PSA, thus leading to more downstream procedures and tests, and treatments; with unclear survival benefit. The *rationale* for this aim is that successful completion of the proposed research will contribute novel, currently unavailable, data to inform patient decision-making.

Comparators [RQ-5]: We selected our comparators of surveillance frequency based on published recommendations and by engaging diverse stakeholders (including clinicians who specialize in prostate cancer care). The three most common surveillance frequencies in clinical

practice are every 3, 6, or 12 months. In each of the 6 patient groups, patient outcomes of every 3 vs. 6 vs. 12 month surveillance will be directly compared. We will define our surveillance groups based on the number of PSA tests patients receive during the first year following completion of prostatectomy or radiation therapy (Figure) – using an “intention to treat” approach – and analyze patient outcomes from Years 2-10. Operationally, we will compare the outcomes of patients who have 1 vs. 2-3 vs. ≥ 4 PSA tests within the first year. We selected this timeframe as we believe that these patterns would be reflective of the physician’s intended surveillance schedule as opposed to later years which may be more reflective of patient adherence to surveillance recommendations.

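### Recurrence can be dated only at a PSA test and the groups differ in how often they are tested, so the time-to-recurrence comparison mixes detection timing with true recurrence timing; the bias is modest and its sign uncertain

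*Combined protocol and SAP*

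**What the plan says.** All of this is in the combined protocol and SAP, mostly under Specific Aim 1.

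- **Exposure (Comparators).** The schedules of interest are "every 3, 6, or 12 months". In practice, "we will compare the outcomes of patients who have 1 vs. 2-3 vs. ≥ 4 PSA tests within the first year". Year 1 was chosen because it should show the physician's intended schedule, unlike "later years which may be more reflective of patient adherence to surveillance recommendations".
- **Outcome (Outcomes).** Time to recurrence is secondary; overall survival is primary. The registry supplies a recurrence date. The special study is to confirm it: "the PSA dates and results will be abstracted from medical records", so that the standard definitions of biochemical recurrence can be applied.
- **Analysis (Data Analysis).** For the secondary outcomes, "time to recurrence will be modeled for each surveillance frequency using a competing risk analysis", with the Fine and Gray method named. Recurrence is also an outcome in the modified Poisson models. On the window: "All outcomes will be defined from years 2-10 from end of prostatectomy or radiation treatment". The section does not say what happens to a recurrence detected in year 1.
- **Sensitivity analyses (Comparators, Potential problems, C3).** These vary the exposure grouping, the adjustment for confounding, the handling of patients treated before they met the recurrence definition, and missing data.

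**The concern.** A PSA-defined recurrence becomes visible at the first test that shows it. If one group is tested every 3 months and another every 12, the recorded date lags the true date by different amounts. A Fine-Gray model on the recorded date treats that difference in lag as a difference in recurrence. This is a measurement problem in the outcome, so propensity scores, instrumental variables and bounds for an unmeasured confounder do not remove it. It would remain even if the groups were exchangeable.

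The year-2 start adds a second mechanism. A recurrence that arises in year 1 may be found before the window opens under frequent testing, but may be carried into the window if a patient's only year-1 test came before it arose. The lag makes frequent testing look worse, and the carry-over makes it look better.

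What is at stake is the interpretation of a secondary outcome. A reader could take a modest hazard ratio between schedules as showing that one group truly recurred more or earlier.

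**Working it through.** The plan gives no figure for time to recurrence, so there is none to reproduce. The check sets true recurrence identical in all groups and asks what the recorded dates would show.

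**Inputs from the document:** intervals of 3, 6 and 12 months; recurrence risks of below 10% (10% used), about 30% and about 50% for low, intermediate and high risk; 14,000 / 6 = 2,333 patients per cohort; the Table 2 group shares; 10-year survival of 70-80%.

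**Assumptions, not in the document:** the recurrence risks apply at 10 years; the hazard is constant (Weibull shape 1.0) or early-peaking (shape 0.7, with 0.6 in a second set of runs); intervals persist after year 1 unless stated otherwise.

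**Step 1, delay.** Mean delay is half the interval: 12/2 = 6, 6/2 = 3 and 3/2 = 1.5 months. The gap between the extreme groups is 6 − 1.5 = 4.5 months.

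**Step 2, apparent incidence gap.** With a constant hazard λ = −ln(1 − F)/10 per year and delay d in years, detected incidence at t is 1 − exp(−λ(t − d)). For high risk, λ = −ln(0.5)/10 = 0.0693. At 2 years, 3-month testing gives 1 − exp(−0.0693 × 1.875) = 12.2% and 12-month testing gives 1 − exp(−0.0693 × 1.5) = 9.9%, a gap of 2.3 points. The same formula gives these gaps in percentage points:

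| Risk group | 2 years | 5 years | 10 years |
|---|---|---|---|
| Low | 0.4 | 0.4 | 0.4 |
| Intermediate | 1.3 | 1.1 | 1.0 |
| High | 2.3 | 1.9 | 1.3 |

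**Step 3, hazard ratio by simulation.** Each recurrence was dated at the next test. The ratio is 3- versus 12-month testing, so a value above 1 makes frequent testing look worse. Recurrence was 30-50% at 10 years and the shape 0.7 or 1.0.

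- From end of treatment: about 1.03-1.07.
- Years 2-10, with the plan's rule of 1 versus ≥4 year-1 tests applied and tests close to schedule: about 1.01-1.08.
- Years 2-10, with the single year-1 test at a random time in that year: about 0.94-0.95 with an early-peaking hazard, and about 1.00 with a constant hazard.

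The years 2-10 range is therefore about 0.94-1.08. Where it falls depends on when the single test occurs and on the hazard shape, and the document gives neither.

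**Step 4, competing deaths and drift in testing.** A second set of high-risk runs used Table 2 group sizes (397, 1,237 and 700), 25% deaths at 10 years, and shape 1.0 or 0.6. In the base case (constant hazard, tests on schedule, year-2 start), mean detected time was 64.5, 61.1 and 59.7 months for 12-, 6- and 3-month testing. At month 120, when all groups had a test, incidence was 41.1% in each. The 12- versus 3-month subdistribution ratio was 0.97, which inverts to 1/0.97 = 1.03, and the false-positive rate was 7.5%. Across the runs with persistent intervals the ratio was 0.93-1.11, which inverts to 1.08-0.90, and the false-positive rate was about 5-11%. If all groups moved to 6-month testing after year 1, the bias nearly vanished with tests on schedule and a constant hazard (0.99-1.01). Carry-over from year 1 could still give 1.07-1.14, which inverts to 0.93-0.88, with false-positive rates of 8-22%.

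**The case against.** The strongest reply is that detected recurrence is what the investigators mean to study. The introduction to Aim 1 gives detection as the purpose of surveillance, and Aim 2 hypothesizes that more testing will find more recurrences. On that view earlier detection is the effect of interest and modeling it away answers another question. This is a good reason to keep the Fine-Gray analysis. It does not remove the problem, because the outcome is named time to recurrence, is tied to standard definitions, and nowhere carries the narrower label.

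The second reply is that the effect is small. That stands. The low-risk gap is 0.4 points, one realistic setting gives a ratio of about 1.00, and groups are fixed on year 1 only, so later intervals may converge. Convergence does not reliably help, however, as Step 4 shows.

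A reader might also infer that the year-2 start reverses the comparison because annual patients routinely carry year-1 recurrences into year 2. The plan's groups do not support this as a general result. If the annual test is scheduled around month 12 with some scatter, about half of those patients are first tested after month 12. They then have no test in year 1 and belong to none of the three groups. With the 1 versus ≥4 rule applied and tests near schedule, the ratio stays at or above about 1.01. At 50% recurrence and shape 0.7, detection in year 2 is about 7.4% with 3-month testing against 4.2% with 12-month testing. A reversal appears only if the single test can fall well before month 12 and recurrence peaks early.

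**Conclusion.** The point holds as a limit on interpretation. The exposure partly sets the recorded date of the outcome, and nothing in the plan deals with this. With persistent intervals, 30-50% recurrence at 10 years and Weibull shape 0.7 or 1.0, the 3- versus 12-month hazard ratio under identical true recurrence is about 1.03-1.07 from end of treatment and about 0.94-1.08 in years 2-10. A steeper early hazard, or convergence of intervals after year 1, can push it somewhat below 0.94. Because the sign depends on facts that the document does not give, a reader cannot correct for it by eye.

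Two stronger readings are not supported. One is that groups with the same true recurrence are bound to look different: the bias can be close to zero under a constant hazard, and at these sample sizes a null comparison would usually not reach significance. The other is that the survival comparison is compromised: death is not dated by PSA testing. This is a change worth making to a secondary analysis and does not threaten the main result.

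**What to change.** 1. Keep the Fine-Gray analysis, label it *time to detected recurrence*, and state that a difference between groups will not be read as a difference in true recurrence.
2. Add an interval-censored competing-risk analysis in which each recurrence lies between the last PSA that did not meet the definition and the first that did, with death as the competing event.
3. State how recurrences detected in year 1, and intervals that straddle month 12, enter the years 2-10 window, and apply the same rule to all groups.

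No new data are needed, since PSA dates and results are already to be abstracted. The cost is a less familiar model, repeated in six cohorts, and somewhat wider confidence intervals. The model also assumes that test times carry no information about recurrence beyond the covariates, which should be stated. Its performance was not simulated here, so it is best added as a sensitivity analysis beside the existing one. Items 1 and 3 need only changes of wording.

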Several outside/environmental factors can affect a patient's surveillance frequency. In our preliminary analysis using the US population-based Surveillance, Epidemiology and End Results (SEER)-Medicare dataset, we found race, marital status, and regional socioeconomic determinants (high school graduation rate) to be associated with different PSA surveillance frequencies. The NCDB captures a comprehensive list of covariates (see above). We will examine if surveillance frequency is associated with each individual factor and account for these factors using modeling as above. Finally, we recognize that there may still be important unmeasured confounders in our study; therefore, we plan to use sensitivity analyses to estimate the impact of a hypothetical unmeasured/unobserved confounder, using similar methodology used in a prior study by the co-I ([name]).²² This analysis will allow us to determine the extent of confounding that would substantively change our study findings.

A conceptual diagram (directed acyclic graph) demonstrating the relationship between measured covariates and our selected study outcomes for Aim 1 is provided in Figure 2 below.

Figure 2. Directed Acyclic Graph for the Hypothesized Relationship between Selected Study Variables and Outcomes for Aim 1

Footnote: Analyses will be stratified by the type of initial treatment (surgery, radiation) and recurrence risk (low, intermediate, high) and the hypothesized relationships may vary somewhat by each clinical scenario. Relationship between variables identified as pertaining to Aim 2 are noted in Figure 3.

Statistical power: There are >1,400 CoC-accredited hospitals. With 10 patients sampled at each hospital, we expect 14,000 patients will be available for analysis. We will intentionally sample approximately the same number of patients in each of the 6 cohorts (risk group x primary treatment), providing 2,333 patients in each cohort. Within each cohort, patients receiving different surveillance frequencies will be compared. Based on preliminary analysis of SEER-Medicare data, the national patterns of PSA surveillance in the first year are: (Table 2)

Number of PSAs	Low Risk	Intermediate Risk	High Risk
1	20%	18%	17%
2-3	61%	59%	53%
4	19%	23%	30%

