Power calculations used a range of 10-year overall survival rates from 70-80%, $\alpha=.05$, and two-sided test. Using distributions in Table 2, there is >80% power to detect a 5% survival difference among groups of different surveillance frequencies. Our stakeholders have indicated this level of survival difference to be meaningful.

Potential problems and alternative strategies:

Although the analysis will stratify by prostate cancer risk status, it is possible that within each

risk strata, patients with clinical and pathological features that are associated with a worse prognosis may be followed more frequently than patients with a better prognosis. One way we have proposed to address this issue is with instrumental variable analysis (Page 11). We will test two commonly-used, potential instrumental variables: region and the provider's most commonly used surveillance regimen (commonly called “provider preference”). Another way to address this in our primary analysis is to account for risk variables (clinical and pathological features) within each risk strata. We will plan to incorporate this in the primary analysis as control variables within the outcome models or within the propensity score model, as appropriate to the research question.

Our definition of comparison groups is based on published recommendations and stakeholder guidance. However, schedules for surveillance PSA tests in this observational cohort may not precisely match the anticipated 3, 6, and 12 month intervals. Multiple classification schemes will be assessed for characterizing the surveillance intervals, as described on page 2. The analysis will be repeated using alternative classification schemes, and sensitivity analyses will be used to determine if there are meaningful differences in the results based on classification of surveillance intervals, and to optimize our classification of surveillance frequency [IR-5].

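### Aim 1 power is based on 10-year survival, but deaths count only from Year 2 to the earlier of Year 10 or end-2015, so the power input overstates the deaths available

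*Combined protocol and SAP*

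**What the plan says.** The Statistical power paragraph of Specific Aim 1 gives the survival input: "Power calculations used a range of 10-year overall survival rates from 70-80" percent. It concludes that "there is >80% power to detect a 5% survival difference among groups of different surveillance frequencies". It names no test, contrast, hazard shape, expected number of deaths or starting point for the 10 years, and it mentions no allowance for incomplete follow-up.

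The Data Analysis paragraphs of the same aim set the window: "All outcomes will be defined from years 2-10 from end of prostatectomy or radiation treatment". The Comparators paragraph agrees, since Year 1 is used to classify men by number of PSA tests. Men diagnosed in 2005-2007 are included, and "By the time of data analysis, the NCDB will have survival data through 2015, providing 8-10 years of follow-up data for each patient".

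The paragraphs also fix the size of each comparison: "providing 2,333 patients in each cohort" and "thus, 6 separate analyses will be performed". Table 2 gives the shares with 1, 2-3 and 4 PSA tests: 20/61/19% (low risk), 18/59/23% (intermediate) and 17/53/30% (high).

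**The concern.** A 10-year survival of 70-80% means that 20-30% of men die over ten complete years. Two parts of that total are not available to the analysis:

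- **Year 1.** Deaths in the first year after treatment fall before the outcome window opens.
- **After 2015.** The clock starts at end of treatment, so a man diagnosed after the start of 2006 cannot complete ten years by the end of 2015. With diagnosis dates spread evenly over 2005-2007, that is about two thirds of the sample.

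The precision of a Cox comparison depends on observed deaths, so power computed from the 10-year total is too high. Overall survival is the primary outcome. The Aim 1 hypothesis expects a survival gain only in high-risk disease, so readers need to know what difference a null result in the other cohorts could have excluded. A restated power figure that kept the 10-year input would carry the same overstatement.

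**Working it through.** **Inputs.** From the documents: 2,333 men per cohort, Table 2 shares, 10-year survival S(10) of 70, 75 or 80%, a 5-point difference, two-sided 5% level, window Years 2-10, diagnosis 2005-2007, data through 2015. Assumed: constant hazard, uniform diagnosis dates (8 to 11 years from diagnosis to end-2015), a gap g of 0 to 0.5 year from diagnosis to end of treatment, no loss to follow-up.

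**1. The plan's own figure, with all 10-year deaths.** Hazard ratio HR = ln S₁ / ln S₂. Power = Φ(|ln HR| √[D p(1−p)] − 1.96), where D is total deaths and p is one group's share of the pair.

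Best case (high risk, 2-3 v 4 tests, 75 v 80%):
- Men: 0.53 × 2,333 = 1,236 and 0.30 × 2,333 = 700.
- Deaths: 1,236 × 0.25 + 700 × 0.20 = 309 + 140 = 449.
- HR = 0.2877/0.2231 = 1.289, ln HR = 0.254; p(1−p) = 0.231.
- 0.254 × √(449 × 0.231) = 2.59, so power is about 73%.

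Over all pairs, risk groups and both 5-point contrasts, power is 40-73% by log-rank (39-72% comparing two proportions). The stated figure above 80% is not reproduced for a pairwise 5-point difference. It is exceeded on some other readings, for example a three-group log-rank test at 70/75/80%, which gives 90-94% but assumes a 10-point spread.

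**2. Share of men whose death is observed.** This is the mean of S(1) − S(min(10, F − g)), with F uniform on 8 to 11 years. For S(10) = 0.75 the hazard is h = 0.02877 per year, and with g = 0:
- S(1) = 0.9716, so Year 1 deaths are 0.0284/0.25 = 11.3% of the 10-year total.
- One third of men reach Year 10 (S = 0.7500). For the rest, mean S over years 8-10 is (0.7944 − 0.7500)/(2h) = 0.772.
- Observed share = 0.9716 − (0.7500/3 + 2 × 0.772/3) = 0.207.
- 0.207/0.25 = 0.828, so 17.2% of deaths are lost: about 11% in Year 1 and 6% after 2015.

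The same formula at S(10) = 0.80 gives an observed share of 0.166.

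**3. Best case again, in the actual window.** Deaths are 1,236 × 0.207 + 700 × 0.166 = 256 + 116 = 372. Then 0.254 × √(372 × 0.231) = 2.35, and power falls from 73% to 65%.

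**4. All cohorts, pairs and contrasts (log-rank).**

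| Scenario | Deaths lost | Fall in power |
|---|---|---|
| Constant hazard, 8-11 years, no gap | 17% | 6-8 points |
| Same, 6-month gap | 21% | 7-10 points |
| Constant hazard, 8-10 years as printed, no gap | 20% | 7-10 points |
| Same, 6-month gap | 25% | 8-12 points |
| Rising hazard (Weibull shape 1.5), 8-11 years, no gap | 12% | 4-6 points |

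In the first two rows, pairwise power ends at about 33-65%.

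**5. A design with exactly 80% power.** Φ(2.80 × √(1 − loss) − 1.96) is about 75% at a 12% loss and 68% at a 25% loss.

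**6. Time at risk from the start of Year 2.** The maximum is 10 − 1 = 9 years. With no gap the range is 7-9 years, with mean (10/3 + 2 × 9/3) − 1 = 8.3. With a 6-month gap the range is 6.5-9 years and the mean about 8.0.

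**7. Binary model.** If its unstated interval ended at Year 8, so that with no gap every man was fully observed, 29-30% of deaths would fall outside it and two-proportion power would drop by 10-18 points.

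**The case against.** Four points on the other side carry weight.

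- **The size rests on assumptions.** Hazard shape, diagnosis-date distribution and treatment gap are not in the documents, so no single percentage can be given as fact. This stands, and is why ranges are shown. Every scenario examined loses deaths.
- **The time origin of the 10-year rate is unstated.** If every man analysed is alive at the start of Year 2, the log-rank fall is about 5-7 points (constant hazard, 8-11 years). If the rate was itself meant for the Year 2-10 window, the Year 1 loss largely disappears. Truncation at end-2015 remains in both cases.
- **A reader might infer that this loss takes power below 80%.** The documents do not support that, because they claim only more than 80% and name no test or contrast. On the three-group 70/75/80% log-rank reading, power goes from 90-94% to 83-89% (constant hazard, 8-11 years, no gap). Only the harshest scenario, 8-10 years with a 6-month gap, brings it to the threshold, at 79-85%. On pairwise readings power is already short with every 10-year death counted, so this loss did not create that shortfall.
- **Cox is not the only primary model.** Section C3 gives modified Poisson/binomial regression the same primary status. The 6-10 points therefore apply to the Cox/log-rank comparison only; the binary model can lose more.

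**Conclusion.** The mismatch is real and lies within the plan's own text: the power input counts ten full years of deaths, while the analysis window omits Year 1 and stops at end-2015. With a constant hazard, uniform diagnosis dates, Year 1 deaths removed, a Year 10 cap, no loss to follow-up and a 0-6 month gap, about 17-21% of the 10-year deaths are lost and pairwise log-rank power for a 5-point difference falls by about 6-10 points. Across the hazard shapes and follow-up ranges tried, the loss is about 12-25% of deaths and 4-12 points. Loss to follow-up would add to this. The finding is that the stated power is overstated by an amount the plan should calculate. It is not proof that power is under 80%. It adds to the separate problem that the stated power is not reproduced for a pairwise 5-point difference.

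**What to change.** In the Statistical power paragraph of Specific Aim 1:

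- State the time origin of the survival rate, and the test and contrast to which the power applies.
- Replace the 10-year input with expected deaths, per cohort and surveillance group, from the start of Year 2 to the earlier of Year 10 or end-2015. State the assumed hazard shape, treatment gap and loss to follow-up.
- Restate power, or the detectable hazard ratio, from those deaths. Do the same for the modified Poisson/binary model from the matching risks, with its interval defined.

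In the Data Analysis paragraph, replace the stated follow-up with the time at risk the analysis uses: at most 9 years from the start of Year 2, roughly 6.5-9 years with a mean of about 8.0-8.3 under a 0-6 month gap.

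The cost is one recalculation and two revised sentences, with no new patients or data. The stated power becomes less favourable.
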